### **9.3.7. Final visit: Home perception questionnaire (caregiver)**

Once the caregiver has indicated that the child has completed their 7 days of wearing the activity belt, study personnel will schedule a clinic visit at the convenience of the participant and their caregiver. If the participant is unable to travel to the clinic, a home visit can be arranged instead. During the final visit, the participant's caregivers will participate in the Home Perception Questionnaire (Form 4) in the form of an interview conducted by study personnel. This questionnaire consists of questions pertaining to the caregiver's perception of the adequacy of facilitating physical activity, safety, and cleanliness inside and outside of the home. This questionnaire will also capture the known physical activity risk factor: screen time . In addition, this questionnaire will collect information on food security, a potential risk factor for low hemoglobin levels, and iron supplement usage. The Home Perception Questionnaire will be conducted during the final visit as opposed to the initial visit in order to avoid influencing the caregiver and effect how the participant wears the activity belt during the accelerometry data collection period.

The caregivers of the participants can opt out of the home perception questionnaire, if they choose to, without penalty.

In addition, child participants within the study will have the opportunity to participate in a general physical checkup during the final clinic visit by our study physician. Participation in the general physical is not mandatory, but is offered as a health incentive to participate in the final visit of the study.

#### **9.3.8. Final visit: Hemoglobin concentration collection (child)**

Hemoglobin concentration will be collected from the child participant one time during the final visit in the clinic (or the home if needed). The study physician or paramedics will ensure that the child is in a seated position before proceeding to clean the child's left index finger with an alcohol wipe. They will proceed to prick participant's left index finger with a spring-loaded needle. Squeezing from the base of the finger to the tip, the research personnel will then encourage blood to flow out of the participant's finger. In order to prevent an inaccurate hemoglobin reading, the first drop of blood will be wiped away with the alcohol swap and the squeezing process will repeat. Once a second drop of blood emerges from the participant's finger, a hemoglobinometer (HemoCue, Helsingborg, Sweden) will be used to collect the drop of blood and provide a hemoglobin concentration reading (to be documented in Form 4).

If an individual has a reading  $<110$  g/L, therefore indicating mild anemia, the study physician will be informed. The individual will then be referred to the local clinic to be evaluated by a physician. The Physician Referral Log will keep track of all anemic participants, date of referral, whether the participant accepted or declined the referral, date of physician appointment, if the participant attended appointment, treatment dosage, and reimbursement amount. If iron supplements are prescribed, we will reimburse the participant the amount spent on the treatment. Detailed instructions will also be provided to the caregiver on the use and safe storage of the supplements.

If an individual has a reading  $<90$  g/L, therefore indicating moderate or severe anemia, the study physician will be informed. As stated above, the individual will then be referred to the local clinic to be evaluated by a physician. All cases of anemia will be documented on Form 4 and will be brought to the supervisor's attention, then included in the Physician Referral Log. The Student Investigator will ensure that the study physician follows up with these participants, and provides reimbursement for any iron supplements prescribed for treatment.

This measure was designed to be collected post accelerometry collection in order to prevent any potential influence iron supplements may have on the participant's physical activity, specifically for those identified with anemia.

An individual has the right to refuse participating in the hemoglobin concentration collection, and will not be penalized for declining this aspect of the study. They will not be included in analyses involving individual hemoglobin concentrations.

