Total number of stationary gross-motor activity items	Count (all integers between 0 and 10); discrete	
Data required:
 
 
• Form 3: Questions 17b-c, 18b-c, 19b-c, 20b-c, 21b-c, 22b-c, 23b-c, 24b-c, 25b-c, 26b-c
 
• The number of incidences where both the 'b' question = 2 AND the 'c' section = 2 (e.g., 17b = 2 AND 17c = 2, this indicates that this item is a stationary gross-motor activity item)
 
 
The number of items that satisfy the above rules will be added together to provide this score. The minimum score is 0 items, with a maximum score of 10 items.

Total number of portable gross-motor activity items	Count (all integers between 0 and 10); discrete	
Data required:
 
 
• Form 3: Questions 17b-c, 18b-c, 19b-c, 20b-c, 21b-c, 22b-c, 23b-c, 24b-c, 25b-c, 26b-c
 
• The number of incidences where both the 'b' question = 1 AND the 'c' section = 2 (e.g., 17b = 1 AND 17c = 2, this indicates that this item is a portable gross-motor activity item)
 
 
The number of items that satisfy the above rules will be added together to provide this score. The minimum score is 0 items, with a maximum score of 10 items.

Hemoglobin concentration	g/L; continuous	Hemoglobin concentration data collecting in Form 4: Q24.

Table 2 - List of additional continuous covariates and their derivation

Variable	Unit	Derivation
Body mass index (BMI) (caregiver)	kg/m 	
Data required (Form 2: Q10-13):
 
 
• Height (m; average of 2 closest height measures)
 
• Weight (kg; average of 2 closest weight measures)
 
 
BMI will be calculated using the formula:  <math>BMI = \text{weight}/\text{height}^2</math>

Body mass index (BMI) z-score (child participant)
	
(z-score)
	
Data required (Form 2: Q1-4):
 
 
• Height (m; average of 2 closest height measures, value will be adjusted by subtracting 0.7 cm if recumbent length was measured)
 
• Weight (kg; average of 2 closest weight measures)
 
 
Height and weight will be plotted on the WHO body mass index-for-age (BMI-for-age) chart (sex specific; ages 2 to 5 years) to determine participant BMI z-score.

Waist circumference
	
cm
	
Average of the 2 closest waist circumference measures (Form 2: Q5,6,14,15)

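### The hemoglobin sampling step wipes the puncture with alcohol and squeezes again just before the single measured drop, which can dilute the reading

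*Combined protocol and SAP*

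**What the plan says.** Section 9.3.8 sets out the sampling sequence. Staff "clean the child's left index finger with an alcohol wipe" and prick it. Then: "Squeezing from the base of the finger to the tip, the research personnel will then encourage blood to flow out of the participant's finger". The reason for discarding the first drop is given as "In order to prevent an inaccurate hemoglobin reading", and the method is that "the first drop of blood will be wiped away with the alcohol swap and the squeezing process will repeat" (the word is evidently swab; section 13 also names the alcohol swab, for infection control). The measured drop is the one straight after: "Once a second drop of blood emerges from the participant's finger, a hemoglobinometer" takes it up.

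There is one measurement occasion: "Hemoglobin concentration will be collected from the child participant one time during the final visit in the clinic", or at home if needed. Table 1 of the Appendix derives the analysis variable directly from that entry: "Hemoglobin concentration data collecting in Form 4: Q24".

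The value has three uses. It is the exposure in Objective 3 (sections 7, 10.2 and 10.4.1). It supports the anemic and non-anemic strata in Objectives 1 and 4 (section 10.4.1). Readings below 110 g/L or below 90 g/L lead to referral (section 9.3.8).

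**The concern.** By discarding the first drop, the protocol accepts that the handling of the drop affects the reading. The way it discards that drop works against this purpose: a wet swab goes back onto the open puncture, the finger is squeezed a second time, and the very next drop is read. Any liquid left at the puncture can mix with that drop. Squeezing of unstated force can add tissue fluid. Either would lower the concentration, by an amount that may differ from child to child.

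Hemoglobin also has less protection than the other physical measures in the plan. Height, weight, waist circumference and bioimpedance (section 9.3.3) are taken in duplicate with repeat-if-discrepant rules, and room dimensions (section 9.3.4) are taken in duplicate. Bioimpedance problems from an uncooperative child are recorded and the affected measures excluded. Nothing comparable is described for hemoglobin.

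At stake are the anemia classification, the number of referrals and, under a further condition, the strength of the Objective 3 association.

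**Working it through.** **Reading the sequence.** The steps in section 9.3.8 are: alcohol clean, prick, first squeeze, alcohol wipe of the first drop, second squeeze, reading of the second drop. No drying is stated after either use of alcohol, and no drop is let go between the second wipe and the reading. Later steps would not recover a low value. The Objective 3 data review in section 10.4.1 looks for outliers and biologically implausible values. Double entry and the missing-data rules address transcription and gaps. A plausible reading a few g/L too low passes all of these.

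**No figure to reproduce.** The plan gives no mean, SD, error or sample size for hemoglobin. The only sized quantity, the ±2.45 cp15s margin in section 9.6, does not involve it. Everything below is an illustration on assumed inputs.

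**Effect of a common dilution on anemia status.** Section 10.4.1 does not define the anemic stratum separately, so I use the 110 g/L limit of section 9.3.8. Assume true hemoglobin is normal with mean 115 and SD 10 g/L, and every reading is lowered by a proportion d. A true value below 110/(1 − d) then reads below 110, so the share read as anemic is Φ[(110/(1 − d) − 115)/10].

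| d | True value that reads as 110 g/L | Share read below 110 | Of 60 children |
|---|---|---|---|
| 0 | 110.0 | 30.9% | 18.5 |
| 1% | 111.1 | 34.9% | 20.9 |
| 2% | 112.2 | 39.1% | 23.5 |
| 3% | 113.4 | 43.7% | 26.2 |
| 5% | 115.8 | 53.1% | 31.9 |

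With the assumed mean varied over 110-120 g/L and the SD over 10-12 g/L, a 2% dilution adds about 6 to 9 percentage points. The classification is sensitive because, under these assumptions, many children lie close to the limit.

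**Effect on the Objective 3 slope.** There are two cases.

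- *Same error in every child.* A constant subtraction leaves the linear slope unchanged. A constant proportional dilution multiplies it by 1/(1 − d), for example 1/0.95 = 1.05 at 5%. Neither attenuates it.
- *Error that varies at random between children.* If the dilution proportion has SD s, the error SD is about 115s g/L, and reliability is 100/(100 + (115s)²). For s = 2%: 115 × 0.02 = 2.3, and 100/(100 + 5.29) = 0.95. For s = 4%: 115 × 0.04 = 4.6, and 100/(100 + 21.16) = 0.83. The slope shrinks by about 5% and 17%. Allowing also for a mean dilution of 5% at s = 4% gives a factor of about 0.85, so the simple formula slightly overstates the loss.

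**The case against.** The strongest reply is that the documents state neither the mechanism nor its size. Section 9.3.8 does not say what makes the first drop unreliable. How wet the swab is, how long staff wait and how hard they squeeze are all unstated. The study physician or paramedics take the sample, and a protocol paragraph need not list every step of their practice. Form 4 is not among the pages available. All of this stands. That residual liquid and squeezing can dilute a drop is general measurement reasoning, so the point goes no further than *can*.

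It does not remove the point. The alcohol wipe and the repeated squeeze are written instructions, not omitted detail, and they precede the only reading.

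The reply also bears on the remedy. Forbidding all squeezing in three-year-olds could increase failed samples, and children who refuse are left out of the hemoglobin analyses. Dropping children who were hard to bleed could select on a trait related to activity. A late change of technique would put two methods into one small dataset: version 1.4 is dated April 2018, in a study planned to end in August 2018. These objections are sound and shape the fix.

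A reader might infer that restless children are squeezed more, so that the error is correlated with activity. Nothing in the documents supports or excludes that, and the point does not rely on it.

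**Conclusion.** The sampling instruction works against its own stated aim, and no later step in the plan would detect or correct the result. It is worth changing because hemoglobin is the only exposure in Objective 3 and the basis for anemia status.

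A common downward shift would affect the anemia strata and referrals. Attenuation of the Objective 3 slope additionally requires dilution that varies between children. The sizes shown (31% rising to 35-53% below 110 g/L for 1-5% dilution; reliability about 0.95-0.83 for a between-child SD of 2-4%) rest wholly on an assumed mean of 115, an assumed SD of 10 g/L and assumed dilution. They show sensitivity and do not estimate the bias in this study.

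Three stronger readings are not supported. The documents do not show that the readings are in fact diluted, since they give no data on the effect of handling. They do not show that the Objective 3 association must be weakened, since a uniform error would not do that. And the primary result is not at risk: mean cp15s comes from the accelerometer and does not use hemoglobin.

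**What to change.** Revise the procedure in section 9.3.8:

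- After the alcohol clean, let the finger dry before the prick.
- Remove the first drop with dry gauze, not the alcohol swab.
- Replace the repeated base-to-tip squeeze with the lightest pressure that yields a drop.
- Record on Form 4 when firm squeezing was needed, and record the date on which the technique changed.

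Keep all readings in the main Objective 3 analysis. Use the squeezing record and the change date in a sensitivity analysis, for example with an indicator for technique period, and do not exclude the flagged children from the main result. For samples already taken, report the handling as a limitation of Objective 3 and of the anemia strata. If collection is largely complete, that statement may be all that can be done. Leave the referral rules unchanged.

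The cost is a wording change, dry gauze, brief retraining and a Form 4 entry. The downsides are slightly longer sampling, a few drops that may fail to flow and, if the change is made mid-study, two techniques in one dataset.

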#### **9.3.9. Final visit: Collection of accelerometer and GPS logger**

Prior to the final visit, study personnel will remind the caregivers of the participants to bring the activity belt(s) to the clinic for their appointment. They will then collect the activity belts (including the accelerometer and GPS logger) from the participants. Data from both devices will then be downloaded and analyzed accordingly (see Section 9.3.5). Once the activity belt has been received, compensation will be provided to the participant's caregiver for their time, travel, and participation in the study. As compensation for the participants for participating in the study, we will then be translating their PA data into a child-friendly, graphics-based activity report that each participant will receive post-analysis.

This activity report will be explained to the parents. Based on the report, study personnel will either inform the caregiver to either encourage child physical activity levels or maintain current levels for optimal child health.

#### **9.4. Expected study duration (for each participant)**

The caregivers of the participants will be contacted for recruitment prior to their anticipated home visit. Study personnel will arrange a convenient time for the participant and their caregiver to conduct the initial home visit.

Each participant will have a minimum study duration of 5 days and a maximum of 15 days. This will include: the initial home visit on Day 1; between 7-14 consecutive or non-consecutive days of wearing the activity belt (accelerometry and GPS logging); and the final visit in the clinic, which will occur once the participant has worn the activity belt for at least 4 days.

The initial home visit is expected to last between 1-2 hours. Each daily phone call is expecting to be between 5-15 minutes each day. The final home visit is expected to last between 1-1.5 hours minutes.

## **9.5. Participant removal criteria**

Participants will be removed from the study if any of the following occur:

1. Participant refuses to participate in accelerometry collection (as this is the primary outcome measure of the study);
2. Contact with the participant's caregiver has not been made in over 3 days;
3. Caregiver withdraws participant consent.

## **9.6. Sample size and power calculations**

Given 126 screened children, we expect to enroll up to 75 children in the study. For our primary objective, we will need 60 enrolled children with complete accelerometric data to be able to describe the mean counts/15 sec (cp15s) with a margin of error of  $\pm 2.45$  cp15s, assuming a standard deviation of 9.7 cp15s.

## **10. Analysis**

### **10.1. Outcome measure**

The primary measure of physical activity will be a continuous variable that represents the average total physical activity level of each child, expressed as a mean counts per 15 seconds (cp15s) averaged over all of the child's eligible wear time on all days that meet criteria for inclusion.

Due to the young age of the participants, compliance for a full 7 days may prove to be difficult; therefore we will use 3 days of data as the minimum number of valid days per child. If a child has more than 7 days of eligible wear time, we will include all additional days with sufficient wear time.

Accelerometry data is collected at 30 Hz, meaning that data measures are collected 30 times per second. Activity counts collected within the 30 measures/second are averaged to provide an activity count for that particular second. We will be analyzing the data in sections of 15 seconds, therefore we will be averaging activity counts within 15 second intervals (average 15 data points of activity counts). These 15 second epochs (cp15s intervals that have been analyzed) will be used to analyze physical activity levels by categorizing them into sedentary behaviour (SED; sitting, laying down, etc.), light physical activity (LPA; walking, crawling, etc.), and moderate-to-vigorous physical activity (MVPA; running, jumping, etc.) using the cut-points chosen.

We will use the cut-points established by Trost and colleagues:  $\leq 48$  cp15s for sedentary behaviour (SED), 49-418 cp15s for light physical activity (LPA), and  $>418$  cp15s for moderate-to-vigorous physical activity (MVPA) . These cut-points were chosen because they were derived from direct observation of a sample of toddler and preschool-aged children while wearing the ActiGraph GT1M accelerometer . Videos of the children playing were coded using a modified version of the Children's Activity Rating Scale before receiver operating characteristic curve analyses were conducted to determine the corresponding cut-points to the 3 categories of interest: SED, LPA, and MVPA . These results were found to exhibit excellent classification accuracy . They were then cross-validated against pre-existing cut-points that are established for toddlers and preschoolers, which were not found to be significantly different than the pre-established cut points established by Pate and colleagues  and those established by National Health and Nutrition Examination Survey .

We will then be able to calculate total time (minutes) as well as proportion of time (%) spent in each activity category (SED, LPA, MVPA). The overall mean cp15s for each child will be based on all 15-second epochs that occurred during eligible wear periods from the time that the caregiver indicated the child woke up until the time that the caregiver indicated the child went to sleep at. If this data is missing, we will use eligible wear periods between 8am to 8pm. This mean will exclude non-wear periods as defined above and when the accelerometer was not being worn by the child (based on daily logs collected from the caregivers via afternoon telephone call; Section 9.3.7.).

For each child, we will calculate the mean number of minutes per day and the proportions of the child's total eligible wear time that are classified as SED, LPA and MVPA. We will also determine the proportion of days on which each child reached or exceeded 180 minutes of activity classified as LPA or MVPA, and the proportion of days on which each child reached or exceeded 60 minutes of activity classified as MVPA. These cut-offs are based on the Canadian preschooler physical activity guidelines established by Tremblay and colleagues , as there are no Bangladeshi standards available at present. If Bangladeshi guidelines are released before data analysis and reporting is completed, we will also apply those standards in our analyses.

For each child, we will establish the following parameters related to accelerometry:

- Total duration (minutes) of the potential data collection period on all days on which the accelerometer was instructed to be worn;
- Total eligible wear time (minutes), including data collected while the child was awake (from the time that their caregiver indicated that they woke up until the time that they went to sleep). If this data is not provided, total eligible wear time will be measured between 8am and 8pm. Non-wear periods will be excluded based on the following

criteria:  $\geq 20$  minutes of 0 cp15s allowing for up to 2 minutes of 0-100 cp15s in that period. A given day will be considered eligible for inclusion if there are at least 10 hours/day (600 min) between the indicated time period that the child was awake at, or between 8am to 8pm of wear time for those with missing data, after excluding non-wear periods;

- Total indoor eligible wear time (minutes; excluding non-wear periods as previously defined), based on maternal report;
- Total eligible wear time in or around the home (minutes; excluding non-wear periods as previously defined), based on combination of maternal report and GPS logging. "Around the home" will be defined as occurring in the same building or property of the home (e.g., rooftop, neighbouring apartment in the same building, common areas of the apartment building, private courtyard areas that are on the same property as the home in which the child resides).

For purposes of secondary and sensitivity analyses, we will also estimate for each child:

- Mean cp15s for indoor activity
- Mean cp15s for activity in or around the home
- Mean cp15s on a day that is typically a work day (Sunday through Thursday)
- Mean cp15s on a Friday and/or Saturday (weekend)

For each of the above measures, we will also classify the activity in terms of average daily minutes and proportion of total time spent in SED state, LPA state, and MVPA state. In sensitivity analyses, we will compare the average daily minutes and proportion of total time spent in each activity category across different cut-off points that have been established by various research groups:

- Proportion of time spent in activity categories established by Pate and colleagues (SED:  $\leq 199$  cp15s; LPA: 200-419 cp15s; MVPA  $\geq 420$  cp15s)
- Proportion of time spent in activity categories established by Sirard and colleagues (SED:  $\leq 301$  cp15s; LPA: 302-614 cp15s; MVPA  $\geq 615$  cp15s) Proportion of time spent in activity categories established by Van Cauwenberge and colleagues (SED:  $\leq 372$  cp15s; LPA: 373-584 cp15s; MVPA  $\geq 585$  cp15s)

To address aim 4, we will analyze sleep quality and quantity directly on the nighttime accelerometry wear periods. Sleep data will be measured in 60-second epochs. This is obtained from the same accelerometry file that the activity data is derived from; however, data will be re-integrated into a 60-second epoch file (analyzes number of activity counts in every 60-second period).

Using the manufacturer's add-on to the ActiLife software (ActiLife 6 Full sleep Features Upgrade), we will be able to detect the number of sleep periods as well as the duration and quality of the sleep periods within the accelerometry file for each participant. The software will also detect and describe:

- Time in bed/out of bed (am/pm); duration in bed (hours; min)
- Sleep onset (when sleep commenced; am/pm)
- Total Sleep Time (TST; hours, min)
- Wake After Sleep Onset (WASO; describes how many minutes after sleep onset the participant woke up; min)
- Awakenings (number of awakenings during sleep onset)
- Average awakenings (average duration of awakenings during sleep onset; min)
- Total activity counts during sleep period (cp60s)
- Movement Index (MI)
- Fragmentation Index (FI)
- Sleep Fragmentation Index (SFI)
- Sleep Efficiency (%)

For descriptive statistics, these measures will be averaged over the number of eligible nighttime wear periods for each participant. In extended analyses, each eligible nighttime wear period will be considered as the unit of analysis.

The accelerometry data will either be processed using the software supplied by the manufacturer (ActiLife ver6) or using a published code to analyze raw accelerometer data .

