### 1. Study Summary

Title	Risk factors for low physical activity levels in preschool-aged children in a densely populated urban community in Bangladesh
Short Title	Preschooler Physical Activity Study (PresPA Study)
Design	Cross-sectional observational
Study Duration	1 year (August 2017 – August 2018)
Study site	Dhaka, Bangladesh
Primary Objective	To describe the physical activity levels in preschool-aged children in urban Bangladesh.
Primary Outcome	Preschooler physical activity levels (mean activity counts/15 seconds will categorize activity into: light and moderate-to-vigorous physical activity, and sedentary behavior based on predetermined cut-points).
# of Participants	60
Main Inclusion Criteria	
 
• Child is between 34-38 months of age;
 
• Child and primary caregiver reside in Dhaka or urban environs;
 
• Parent/guardian provides written informed consent for study procedures.
 

Main Exclusion Criteria	
 
• Child requires mobility assistance;
 
• Child has been diagnosed with a neurological disorder affecting physical activity (e.g., Cerebral palsy) or a major chronic respiratory or cardiac disease that limits physical activity (e.g., severe asthma, congenital heart disease).
 

Follow-up period	N/A

Main Study Procedures	
 
1. Accelerometry & GPS logging
 
2. Anthropometry
 
3. Blood hemoglobin concentration test
 
4. Home environment audit
 
5. Home perception questionnaires
 
6. Socioeconomic questionnaires
 

-----------------------	---------------------------------------------------------------------------------------------------------------------------------------------------------------------------------------------------------------------------------------------------------------------------------------

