The accelerometer device will be set to collect data at 30 Hz (i.e., it will take readings 30 times per second) to ensure high-quality data. Data can only be viewed after the device has been collected from the participant and uploaded into the software program (ActiLife v10). Activity is measured in counts, and is analyzed over specified time periods. Once the number of counts has been analyzed over a specified time period, the data point is then referred to as an 'epoch'. Data will be analyzed in 15 second epochs (counts per 15 seconds; cp15s).

The GPS logger will objectively measure the coordinates of each location that the participant travels. As with the accelerometer, the GPS logger device is to be worn continuously for 7 days, or non-consecutively within a 14-day time period. The collection of location data will occur simultaneous to the collection of accelerometry data. To ensure quality location data, the device will be set to take readings every 15 seconds, as this will directly correspond to the 15 second epochs calculated from the processed accelerometry data. This data will be used in combination with the accelerometry data to gain insight on the location of preschooler activity (e.g., home, park, relative's home, street, etc.). Similarly, as with the accelerometry data, data collected from the GPS logger can only be viewed after the device has been collected from the participant and downloaded into the software program (iTrail GPS Mapping and Trip Analysis Software). This passive GPS device does not offer remote real-time tracking; therefore, it cannot provide real-time location data and data can only be collected once the device has been returned.

The data collected from the GPS logger in combination with the accelerometry data will substantially increase the measured accuracy, sensitivity and objectivity of an individual's exposure to environments while they engage in active behaviour. Together, the will

objectively, and accurately, measure the types of environments that individuals are exposed to, the duration they were there for, and what kind of active behaviours they participated in .

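### Section 10.1 builds each 15-second epoch as an average of one-second counts but classifies it with cut-points in counts per 15 seconds

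*Combined protocol and SAP*

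**What the plan says.** Section 10.1 (Outcome measure) builds the epoch in two steps. First, from 30 Hz readings to seconds: "Activity counts collected within the 30 measures/second are averaged to provide an activity count for that particular second". Second, from seconds to epochs: "therefore we will be averaging activity counts within 15 second intervals (average 15 data points of activity counts". It then says what the epochs are for: "These 15 second epochs (cp15s intervals that have been analyzed) will be used to analyze physical activity levels by categorizing them".

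The unit is defined in Section 9.3.5: "Data will be analyzed in 15 second epochs (counts per 15 seconds; cp15s". Everything that meets the epochs afterwards is in that unit:

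- The primary cut-points in Section 10.1 are at most 48 for sedentary behaviour (SED), "49-418 cp15s for light physical activity (LPA", and above 418 for MVPA.
- The three alternative cut-point sets in Section 10.1 are also in cp15s.
- The non-wear rule requires at least 20 minutes of zero counts, "allowing for up to 2 minutes of 0-100 cp15s in that period".

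The Study Summary (Section 1) describes the primary outcome through the categories: "mean activity counts/15 seconds will categorize activity into: light and moderate-to-vigorous physical activity, and sedentary behavior based on predetermined cut-points". Section 10.1 also derives guideline results from them, including the "proportion of days on which each child reached or exceeded 180 minutes of activity classified as LPA or MVPA", with a matching result for 60 minutes of MVPA.

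Section 10.1 leaves processing open between the manufacturer's software and published code for raw data.

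**The concern.** A mean of 15 one-second counts is a rate per second. The cut-points apply to a total over 15 seconds. The two differ by a factor of 15, and no section multiplies the epochs by 15 or divides the cut-points by 15.

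An analyst who codes the written rule and then applies the printed cut-points would misclassify activity. This would affect the minutes and proportions in SED, LPA and MVPA, the 180- and 60-minute guideline results under Objective 1, and the categorised form of the primary outcome in the Study Summary. The non-wear screen would also loosen.

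The continuous mean and the regressions for Objectives 2 and 3 are much less exposed. Dividing every epoch by 15 mainly rescales them, apart from any change in which periods are excluded as non-wear.

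**Working it through.** **The plan's own figure.** Section 9.6 gives n = 60, SD 9.7 cp15s and a margin of ±2.45 cp15s. The confidence level is taken as 95% from Section 10.4.1. Margin = 1.96 × 9.7 / √60 = 2.454, which agrees with the plan. The sample size is stated in cp15s and does not depend on this point. If the outcome were on the averaged scale, the matching SD and margin would be 9.7 / 15 = 0.647 and 2.45 / 15 = 0.163. A mean built as written would therefore not be in the unit of its precision target.

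**Scale of the epoch.** Let T be the total count in 15 seconds. Averaging 15 one-second counts gives T / 15. A printed limit c applied to T / 15 acts as a limit of 15c on T. Only the 15-value average is used here; the averaging of 30 readings within each second is left out.

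| Cut-point set | Printed SED limit | Effective SED limit on T | Printed LPA upper limit |
|---|---|---|---|
| Primary | 48 | 48 × 15 = 720 | 418 |
| First sensitivity set | 199 | 199 × 15 = 2,985 | 419 |
| Second sensitivity set | 301 | 301 × 15 = 4,515 | 614 |
| Third sensitivity set | 372 | 372 × 15 = 5,580 | 584 |

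In every row the effective SED limit lies above the top of the intended light range, so all true LPA becomes SED in all four sets. Comparing cut-point sets would not correct this.

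**Primary set in detail.** The effective MVPA limit is 418 × 15 = 6,270.

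- Totals of 49–418 (true LPA) become SED.
- Totals of 419–720 (true MVPA) become SED.
- Totals of 721–6,270 (true MVPA) are not labelled MVPA. Within these, totals of 721–734 average between 48 and 49 (49 × 15 = 735), in the gap between the printed limits, and are counted here as LPA.

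Examples:

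- T = 100 is LPA, but 100 / 15 = 6.67 is read as SED.
- T = 420 is MVPA, but 420 / 15 = 28.0 is read as SED.
- T = 1,000 is MVPA, but 1,000 / 15 = 66.7 is read as LPA.

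**Guideline results.** An epoch would count towards the 180 minutes only if T exceeds 720, which is 720 / 418 = 1.7 times the intended MVPA limit. It would count towards the 60 minutes of MVPA only if T exceeds 6,270.

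**Non-wear rule.** Zero stays zero after averaging, but the tolerance of 100 acts as 100 × 15 = 1,500 on T. A 20-minute window holds 80 epochs (20 × 60 / 15), and 2 minutes is 8 of them. More windows could therefore qualify as non-wear.

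**The case against.** The best reply is that this is a slip in an explanatory sentence and that the intent can be recovered. Section 9.3.5 speaks of the number of counts over a period and defines cp15s as counts per 15 seconds. Section 10.1 describes the 60-second sleep epoch, from the same file, as the number of counts in each period, which is a total. The outcome definition that opens Section 10.1 uses the same unit. No section describes a manual step that divides software output by 15, so the software may well deliver totals. Section 10.1 also defines the primary measure as a continuous mean, which would mainly be rescaled. Finally, the planned graphs and the comparison with published preschool populations in Section 10.4.1 might expose a gross error.

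Much of this stands. It makes the harm conditional, and it shows that totals are probably what is meant. It does not clear the text. The averaging sentence explicitly refers to 15 data points, so it cannot be read as the later, legitimate averaging of epochs over wear time. The processing paragraph offers two routes and does not say that either replaces the averaging rule. A comparison with other populations might raise suspicion, but it would not identify the cause, and a real difference between settings could look similar.

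**Conclusion.** The concern holds. The rule for building the classified epoch is wrong as written: it gives counts per second, while all four cut-point sets and the non-wear tolerance are in counts per 15 seconds. If it is followed with the printed cut-points, the effective primary limits become 720 and 6,270, all true light activity is labelled sedentary, and the category and guideline results are invalid. If the software sums counts, the results are right but the written definition of the outcome is not what was done.

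The factor of 15 is exact for the 15-value average alone. The share of epochs relabelled depends on the distribution of counts, which the documents do not give. The sample size is unaffected, and the Objective 2 and 3 models would be affected mainly in scale. The text should be corrected before the data are processed.

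**What to change.** In Section 10.1, replace the two averaging sentences with wording such as:

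> Activity counts are summed over each 15-second epoch (counts per 15 s). Each epoch total is classified with the cut-points, and the child's mean cp15s is the mean of these epoch totals.

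Add that the non-wear rule uses the same epoch totals. Name the processing route that converts the 30 Hz readings to counts, and state that epoch totals are used on whichever route is chosen. The cut-points require this, because the plan does not say that the raw-data code yields counts.

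The cost is two replaced sentences and one added statement. No new data are needed, and the design, model, cut-points and sample size stay as they are.
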